6.2.6 IKDC

IKDC will be collected at Visits 3, 4, 5, 6, 7 and 8 (Baseline, M1, M3, M6, M9 and M12) or Early Termination (only if the subject is early terminated after Visit 3) or Final Follow-up Visit. Summary statistics of IKDC will be presented by visit and treatment group. The change from baseline will also be calculated and represented in summary table.

① Change of IKDC from baseline at Month 6 (JointStem group vs. positive control group)

This secondary efficacy endpoint will be analyzed with an ANCOVA with factors of treatment and the baseline of IKDC as a covariate. Model-based LS Means of the differences between study and control groups, along with 95% CI and p-value will be provided.

② Change of IKDC from baseline at Months 6, 9 and 12 (JointStem group)

Change of IKDC from baseline at Months 6, 9 and 12 will be analyzed using paired t-test (two-sided test, $\alpha=0.05$) with the null hypothesis equal to zero. The number of patients, mean, standard deviation, minimum (min) and maximum (max) values for the baseline, months 6, months 9, months 12 and change from baseline will be calculated and reported in summary table. The 95% CI and p-value will also be provided. Shapiro-Wilks test will be used to test the normality of change of IKDC from baseline at Months 6, 9 and 12. If change of IKDC from baseline at Months 6, 9 and 12 doesn't satisfy normal distribution, Wilcoxon signed rank test will be performed.

6.2.7 RAND-36 Score

RAND-36 Score (Physical Functioning, Role Limitation (Physical), Role Limitation (Emotional), energy/Fatigue, Emotional well-being, Social Functioning, Pain, General Health) at Visits 3, 5, 6, 7 and 8 (Baseline, M3, M6, M9 and M12) or Early Termination (only if the subject is early terminated after Visit 3) or Final Follow-up Visit. Summary statistics of RAND-36 Score will be presented by visit and treatment group. The change from baseline will also be calculated and represented in summary table.

- ① Change of RAND-36 Score from baseline at Month 6 (JointStem group vs. positive control group)

This secondary efficacy endpoint will be analyzed with an ANCOVA with factors of treatment and the baseline of RAND-36 Score as a covariate. Model-based LS Means of the differences between study and control groups, along with 95% CI and p-value will be provided.

- ② Change of RAND-36 Score from baseline at Months 6, 9 and 12 (JointStem group)

Change of RAND-36 Score from baseline at Months 6, 9 and 12 will be analyzed using paired t-test (two-sided test, $\alpha=0.05$) with the null hypothesis equal to zero. The number of patients, mean, standard deviation, minimum (min) and maximum (max) values for the baseline, months 6, months 9, months 12 and change from baseline will be calculated and reported in summary table. The 95% CI and p-value will also be provided. Shapiro-Wilks test will be used to test the normality of change of RAND-36 Score from baseline at Months 6, 9 and 12. If change of RAND-36 Score from baseline at Months 6, 9 and 12 doesn't satisfy normal distribution, Wilcoxon signed rank test will be performed.

7. SAFETY ANALYSIS

All safety analyses will be performed for safety population. Statistical tests are not planned for safety variables. Safety assessments include:

- AEs
- Clinical laboratory tests
- ECG
- Physical examinations
- Vital signs

7.1 ADVERSE EVENTS

AEs will be coded by SOC and PT using the MedDRA (Version 18.1). The verbatim term will be included in the AE listing.

A treatment-emergent adverse event (TEAE) is defined as an AE that occur or worsen on or after the injection of study drug and before the end of the study. Only TEAEs will be included in summary tables. All AEs, treatment emergent or otherwise, will be presented in subject data listings.

The TEAEs will be summarized as the number (percentage) of subjects with TEAEs within SOC and PT. Subjects who report the same PT on multiple occasions will be counted once for the PT: under the highest severity (severe > moderate > mild) when summarized by severity and under the closest relationship to study drug when summarized by relationship. If a subject reports multiple PT for a SOC, the subject will be counted only once for that SOC.

TEAEs will be summarized as below.

- An overview table, including number of subjects with
 - TEAEs
 - serious AEs (SAEs)
 - study drug related TEAEs
 - TEAEs by severity
 - TEAEs leading to study discontinuation
 - TEAEs leading to death
- TEAE by SOC and PT
- TEAE by SOC, PT, and Severity
- Study drug related TEAEs by SOC, PT
- SAEs by SOC and PT
- TEAEs leading to study discontinuation by SOC and PT

All AE tables will be sorted by SOC and PT in decreasing frequency of the number and percentage of subjects summarized by treatment group and total.

Missing date will be imputed followed table describes how missing date information will be handled:

| Partial Missing Start or Stop Date | Imputed Start Date | Imputed Stop Date |
|--|--|-----------------------------------|
| Missing month and day, and the year is present | January 1 of that year or first dose date if the year is the same as the year of first dose date | December 31 of that year |
| Missing day, but year and month are present | First day of that month or first dose date if the year and month are the same as the year and month of first dose date | Last day of that month |
| Missing month, but year and day are present | Missing month imputed as January | Missing month imputed as December |

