**Secondary Endpoints:**  
1) JointStem group vs. positive control group  
① Change of WOMAC score from baseline at Month 6  
② Change of VAS score from baseline at Month 6  
③ Change of KOOS from baseline at Month 6  
④ Change of Lysholm Knee Scoring Scale from baseline at Month 6  
⑤ Change of IKDC from baseline at Month 6  
⑥ Change of RAND-36 Score from baseline at Month 6  
2) JointStem group  
① Change of WOMAC score from baseline at Months 9 and 12  
② Change of VAS score from baseline at Months 9 and 12  
③ Comparison of MRI improvement evaluations between at Month 6 and at Month 12  
④ Change of Lysholm Knee Scoring Scale from baseline at Months 6, 9 and 12  
⑤ Change of KOOS from baseline at Months 6, 9 and 12

- ⑥ Change of IKDC from baseline at Months 6, 9 and 12
- ⑦ Change of RAND-36 Score from baseline at Months 6, 9 and 12
- 3) Incidence of adverse events and laboratory abnormalities

**Exploratory Endpoints:** Analysis of all efficacy scales and MRI results and the history of treatments and medications following 2 years after injection for all subjects who are injected and complete 6-month follow-up visit

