## 2. Secondary Endpoints

The comparison of WOMAC score, VAS score, Lysholm Knee Scoring Scale, KOOS, IKDC and RAND-36 score between study and control groups will be analyzed using Analysis of Covariance (ANCOVA) with factors of treatment and baseline of each variable as a covariate.

Model-based LS Means of the differences between study and control groups along with 95% CI and p-value will be provided.

In addition, the change of secondary efficacy variables within study group shall be tested using paired t-test. If the change of score from baseline at each assessment point doesn't satisfy normal distribution, Wilcoxon signed rank test will be performed.

In case of MRI, the frequency and percentage of subjects whose PI evaluation is 'improvement' at Month 6 will be calculated. In addition, MRI improvement evaluation at Month 12 compared to Month 6 will be analyzed using McNemar test or Bowker's test.

Safety variables will be summarized descriptively, by treatment group and visit.

When at least 15 subjects complete 6-month visits (Visit 6, Month 6), one unblinded interim analysis can be performed to evaluate the efficacy and safety of JointStem without the suspension of subject's schedule of assessments. The details of this interim analysis will be presented in the statistical analysis plan.

All efficacy variables and the history of treatments and medications, which are measured at a long-term follow-up visit (24 months after injection) will be analyzed between treatment groups to see any long-term effects of JointStem. Also, MRI results of long-term follow-up visit will be compared to previous MRI results to see any long-term effects of JointStem.

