### Schedule of Assessments

	Screen.	Harv.	Treat.	1 st Follow-up				2 nd Follow-Up		Long-term	
Blinding	N/A	Double Blinding							Open 		Follow-up
Visit	1	2	3	4	5	6	ET	7	8	N/A	
Week / Month	W-7	W-5	0	M1	M3	M6	<M6	M9	M12 or Final FU 	M24	
Informed consent	X										
Medical and Medication History	X	X									
Demographic information	X										
Complete physical examination	X		X		X	X	X 	X	X	X	
Vital signs and weight	X	X	X	X	X	X	X	X	X	X	
Hematology, serum chemistry, and urinalysis 	X		X	X	X	X	X 	X	X		
Pregnancy test 	X					X	X 		X		
HIV test for Screening	X										
12-lead ECG	X		X			X	X 		X		
X-ray	X										
Eligibility confirmation	X	X									
Randomization		X									
Liposuction		X									
Injection of final drug product			X								
AE and concomitant medication assessment			X	X	X	X	X	X	X		
Records of Treatment and Medications										X	
MRI scan 	X					X	X 		X	X	
WOMAC			X	X	X	X	X 	X	X	X	
VAS	X		X	X	X	X	X 	X	X	X	
Lysholm			X	X	X	X	X 	X	X	X	
KOOS			X	X	X	X	X 	X	X	X	
IKDC			X	X	X	X	X 	X	X	X	
Quality of Life (RAND-36)			X		X	X	X 	X	X	X	

1. See Appendix 1 for the complete list of laboratory tests
2. Serum pregnancy test is performed for all females of childbearing potential (please refer to the relevant inclusion criteria)
3. May be performed the day of Visit 2 or after due to scheduling or re-scanning.
4. Performed only if the early termination is after V3.
5. Performed only if the early termination is after V4.
6. Performed if the follow-up is discontinued after V6.
7. Only for JointStem group.

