#### **3.5.3 End of Study**

The efficacy results will be analyzed when the last subject completes Visit 6 (6-month follow-up) and this study is finished when the last subject completes Visit 8 (12-month follow-up).

Long-term follow-up visit will be conducted to collect long-term feedbacks (records of medications and treatments) following 2 years after injection for all subjects who complete 6-month visit and accept the long-term follow-up visit.

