### **3.5.8 Treatment Compliance**

Only subjects who are randomized to JointStem will return on Visits 4, 5, 6, 7 and 8 (Months 1, 3, 6, 9 and 12) or at Early Termination. On the other hand, subjects who are randomized to the positive control group will only return on Visits 4, 5 and 6 (Months 1, 3 and 6) or at Early Termination.

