#### 4.2.7 Visit 7 (Month 9 ± 1 week)

Only subjects who are randomized to JointStem group will visit the clinical site for the following assessments/procedures:

- The following questionnaires/procedures will be completed: WOMAC (see Appendix 3), VAS (see Appendix 4), Lysholm scale (see Appendix 5), KOOS (see Appendix 6), IKDC (see Appendix 7), and RAND-36 (see Appendix 8).
- Measure vital signs (sitting blood pressure, pulse, breathing, and temperature) and weight.
- Record any adverse event and any change in concomitant medications.
- Perform a complete physical examination.
- Collect blood and urine samples for hematology, serum chemistry, and urinalysis.
- Dispense a concomitant medication note.

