#### 4.2.8 Visit 8 (Month 12 ± 1 week)

Only subjects who are randomized to JointStem group will visit the clinical site for the following assessments/procedures:

- The following questionnaires/procedures will be completed: WOMAC (see Appendix 3), VAS (see Appendix 4), Lysholm scale (see Appendix 5), KOOS (see Appendix 6), IKDC (see Appendix 7), and RAND-36 (see Appendix 8).
- Measure vital signs (sitting blood pressure, pulse, breathing, and temperature) and weight.
- Record any adverse event and any change in concomitant medications.
- Perform a complete physical examination.
- Measure 12-lead ECG.
- Collect blood and urine samples for hematology, serum chemistry, and urinalysis.
- Perform MRI measurement (Please follow the collection instruction separately provided by the sponsor).

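### SAP 7.1 compares TEAE percentages by arm although scheduled AE assessment ends at Month 6 in control and Month 12 in JointStem, so late JointStem first events inflate the any-TEAE, SOC and PT comparison

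*SAP*

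**What the plan says.** - **Window.** SAP 7.1 defines a TEAE as one "defined as an AE that occur or worsen on or after the injection of study drug and before the end of the study". Protocol 3.5.3 places that end late: "this study is finished when the last subject completes Visit 8 (12-month follow-up".
- **Statistic.** SAP 7.1 reports the number and percentage of subjects by treatment group and total. Each subject counts once per PT and once per SOC, under the highest severity or closest relationship where those are tabulated. It gives no Month 6 cut, period split or exposure adjustment.
- **Follow-up.** Protocol 3.5.8 states that "subjects who are randomized to the positive control group will only return on Visits 4, 5 and 6". For Months 9 and 12, Protocol 4.2.7 and 4.2.8 say "Only subjects who are randomized to JointStem group will visit the clinical site for the following assessments/procedures", and both visits include the instruction "Record any adverse event and any change in concomitant medications".
- **Month 24.** In the protocol's Schedule of Assessments the row "AE and concomitant medication assessment" has no mark at Month 24, and Protocol 4.2.11 lists no AE assessment there.
- **Intended presentation.** The protocol synopsis says "Safety variables will be summarized descriptively, by treatment group and visit". SAP 7.2, 7.3.1 and 7.3.3 do this for laboratory tests, vital signs and ECG. SAP 7.1 lists no AE table by visit or period, and Protocol 6.1.6 does not mention visit for AE rates.
- **Status.** "Incidence of adverse events and laboratory abnormalities" is a named secondary endpoint in the synopsis and in Protocol 3.6.1.

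**The concern.** The two columns of each TEAE table would cover different lengths of scheduled observation. A crude percentage of subjects with at least one event grows with time watched, so the arm watched longer tends to show more subjects with events even if the treatments carry the same risk.

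The extra period also differs in kind. The blind is opened subject by subject after Visit 6 (Protocol 3.5.6 and 4.2.6), and pain medication for osteoarthritis is then permitted (Protocol 3.5.7). For JointStem alone, the table mixes blinded and open-label reporting.

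At stake is a fair reading of the by-arm AE tables. JointStem could look less safe than control partly because it was observed for longer. The pooled total column would also mix the two windows.

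**Working it through.** **Inputs.** The arms are 20 JointStem and 10 control (SAP 1.3.3), which agrees with 30 subjects at 2:1 (30 × 2/3 = 20; 30 × 1/3 = 10). Scheduled AE assessment runs to Month 12 and Month 6 respectively. No AE incidence or timing is given, so there is no stated figure to reproduce.

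**Observation time.** If all subjects are injected and complete, JointStem contributes 20 × 12 = 240 person-months and control 10 × 6 = 60. That is 4:1 on a 2:1 randomisation.

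**Any-TEAE, SOC and PT rows.** Let a be the JointStem subjects with a first event in the row by Month 6, b those with a first event later, and c the control subjects with an event.

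- Equal-window ratio: (a/20)/(c/10).
- Tabulated ratio: [(a+b)/20]/(c/10).
- Factor between them: (a+b)/a, above 1 whenever b ≥ 1 (for a ≥ 1 and c ≥ 1).
- Percentage difference: it rises by b/20, or 5 points per late subject, whatever the value of c.

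Example: control 2/10, JointStem 4/20 by Month 6, then 3 late first events. The equal-window reading is 20% v 20%, ratio 1.00. The table prints 7/20 = 35% v 20%, ratio 1.75. The total column moves from 6/30 = 20% to 9/30 = 30%.

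**Size under assumed rates.** Assume the same 6-month risk p in both arms, and a JointStem hazard after Month 6 equal to h times the earlier one. The 12-month risk is 1 − (1 − p)^(1+h) and the false ratio is that risk divided by p. With h = 1 the ratio is 2 − p. Extra JointStem subjects are 20 × (12-month risk − p).

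| p | h = 1: ratio (extra subjects) | h = 0.25: ratio (extra subjects) | h = 0 |
|---|---|---|---|
| 10% | 1.90 (1.8) | 1.23 (0.47) | 1.00 (0) |
| 20% | 1.80 (3.2) | 1.22 (0.87) | 1.00 (0) |
| 40% | 1.60 (4.8) | 1.18 (1.4) | 1.00 (0) |

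At p = 20%, the chance of at least one late first event among 20 subjects is 0.97 for h = 1 and 0.59 for h = 0.25. With both arms cut at Month 6, the ratio under equal risk is 1.00 for every p.

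**Severity rows.** Take a mild row with JointStem 4/20 and control 2/10 at Month 6. If two JointStem subjects later have a severe event of the same PT and one new mild case appears, the mild row becomes 3/20 = 15% and its ratio falls from 1.00 to 0.75, while two subjects move to the severe row. The closest-relationship rule works in the same way wherever events are split by relationship.

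**Reading of the end of the study.** Taking it as each subject's own last visit changes nothing: scheduled observation is still Month 12 against Month 6.

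**The case against.** Several objections have force.

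- **No formal comparison is planned.** The protocol lists AE incidence apart from its between-arm endpoints. The SAP prints percentages, not ratios, and plans no safety test (SAP 7). The stopping criteria in Protocol 3.4 use counts or judgement, and all AEs are listed, so a Month 6 cut could be made later. This limits the weight of the point. It does not remove it, because the columns still stand side by side, and a cut chosen after the codes are open is weaker than one fixed in advance.
- **The size is assumed.** The constant-hazard figures may not suit a single injection, and small ratios would be lost in noise: exact 95% intervals are 12% to 74% for 4/10 and 19% to 64% for 8/20. This stands. Only the mechanism comes from the documents.
- **Control events after Month 6 are not excluded.** Protocol 7.2 requires events reported by subjects after the first dose to be recorded and sets no stop date. A spontaneous control report would add 10 points (1 of 10) and could offset the shift. What remains is that control has no scheduled assessment to match Visits 7 and 8. Protocol 3.6.3 collects AEs at all visits after randomisation, but that creates no control visit at Month 9 or 12.
- **Denominators.** The Safety population is based on Visit 2 completion (SAP 2.2.3), so it can include uninjected subjects. The 5 points are therefore approximate.
- **Other tables may exist.** An optional interim analysis covers safety but lies outside this SAP (SAP 8.1), so its tables cannot be assessed.

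A reader might infer that the longer window can only add JointStem subjects to every row, or that the bias always runs against JointStem. The documents do not support that: the highest-severity rule can take a subject out of a milder row, the ratio is undefined when control has no event, and spontaneous control reports remain possible.

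**Conclusion.** The point holds for the any-TEAE, SOC and PT rows. Each late JointStem first event adds about 5 percentage points without a matching scheduled control observation. This inflates the by-arm difference, and the ratio where control has at least one event, relative to an equal window. The severity and relatedness tables are also built on unequal windows, but no direction can be given for a particular row.

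Under equal hazards and full follow-up, the false ratio lies between 1.00 and 2 − p for a later hazard no higher than the earlier one. A reader might take 1.90 as the expected distortion. It is the constant-hazard value at an assumed 10% risk; if events cluster soon after injection, the effect is small or nil.

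The SAE rows cannot be settled. Protocol 7.3 limits collection to the 3-month follow-up in one sentence and refers to the follow-up period in the next. The two must be reconciled.

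A reader might extend the point to the concomitant-medication table in SAP 5.2. That is not supported: the Month 24 visit collects medication records in both arms, the SAP does not say whether they enter that table, and the net effect is unknown.

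This should be fixed before the AE tables are produced, but it touches only a descriptive safety comparison.

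**What to change.** In SAP 7.1:

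1. Restrict the by-arm and total TEAE tables to events with onset or worsening from injection through Visit 6, or the early termination visit.
2. Report later events, up to Visit 8 or the final follow-up visit, in separate JointStem-only tables.
3. Apply the highest-severity and closest-relationship rules within the Visit 6 window as far as the recorded data allow. Protocol 7.2 asks for severity with start and stop dates but does not list dated severity changes, so an event that worsens after Visit 6 may not be separable.
4. Where a start date is incomplete, assign the period from the visit at which the event was first recorded, if the eCRF keeps it. Otherwise the date table can move a Month 7 to 12 event back to the first dose date or to 1 January. Also state that imputation must not place an event first recorded after injection before the injection, unless the known date parts require it. An event with only its month missing is set to January; if that precedes injection, it fails the TEAE definition and reaches neither table.
5. State the SAE window once Protocol 7.3 is reconciled.

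The cost is SAP wording and a second set of JointStem tables. No extra visits are needed and the Safety population is unchanged. The drawback is that JointStem's 12-month incidence must be read from two tables that cannot be added, because one subject can appear in both.

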### **3.6.3 Safety Variables**

- Hematology, serum chemistry and urinalysis at Visits 1, 3, 4, 5, 6, 7 and 8 (Screening, Baseline, M1, M3, M6, M9 and M12) or Early Termination (only if the subject is early terminated after Visit 3) or Final Follow-up Visit. See Section Appendix 1 for a complete list of laboratory tests to be done.
- ECG evaluation at Visits 1, 3, 6 and 8 (Screening, Baseline, M6 and M12) or Early Termination (only if the subject is early terminated after Visit 3) or Final Follow-up Up Visit
- Complete physical examination at Visits 1, 3, 5, 6, 7 and 8 (Screening, Baseline, M3, M6, M9 and M12) or Early Termination (only if the subject is early terminated after Visit 3) or Final Follow-up Up Visit
- Vital signs (sitting blood pressure, pulse, breathing, and temperature) and weight will be measured at all visits.
- Data regarding AEs and concomitant medications collected at all visits after randomization

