##### 6.1.1.3 Safety Population

Any subject who was randomized and completed Visit 2 (Week -5) will be included in the evaluation of safety. This cohort will be evaluated for all safety variables.

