### 6.1.6 Safety Analyses

AE rates will be summarized by treatment group and overall, and will be broken down by severity, seriousness and relation to study drug. Statistical tests are not planned for safety variables.

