2.2.3 Safety Population

A Safety population will include any subject who was randomized and completed Visit 2 (Week - 5, at which time adipose tissue was be harvested).

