7.1.1 Deaths, Serious and Other Significant Adverse Events

The listings of serious AEs, AE leading to study discontinuation, and subjects who died during the study will be provided.

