9. SUMMARY OF MAJOR CHANGES IN THE PLANNED ANALYSES

There is no major change in the planned analyses based on the study protocol (Version 6.0, Apr 7, 2017).

DOCUMENT REVISION HISTORY

| DATE | VERSION | AUTHOR/ UPDATED BY | COMMENTS |
|----------------|---------|--------------------|---------------------------|
| March 15, 2017 | 1.0 | [name] | Initial version finalized |
| April 5, 2018 | 2.0 | [name] | Updated per protocol v6.0 |

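### The Safety population starts at the Visit 2 liposuction but the AE tables start at the injection, and the protocol conflicts on when AE capture begins and when SAE collection ends

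*SAP*

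**What the plan says.** **Population.** Protocol 6.1.1.3: "Any subject who was randomized and completed Visit 2 (Week -5) will be included in the evaluation of safety". SAP 2.2.3 agrees: "A Safety population will include any subject who was randomized and completed Visit 2", and notes that this is the harvest visit. Protocol 3.5.1 and 4.2.1 apply randomization and liposuction to both groups at Visit 2. Protocol 4.2.3 places the injection within 5 weeks of that visit.

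**Analysis.** Protocol 6.1.6: "AE rates will be summarized by treatment group and overall, and will be broken down by severity, seriousness and relation to study drug". It gives no time window. SAP 7.1 defines a TEAE as "an AE that occur or worsen on or after the injection of study drug and before the end of the study" and adds: "Only TEAEs will be included in summary tables". The remaining AEs go to subject listings. SAP 7.1.1 adds: "The listings of serious AEs, AE leading to study discontinuation, and subjects who died during the study will be provided".

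**AE capture.** Protocol 3.6.3: "Data regarding AEs and concomitant medications collected at all visits after randomization". Protocol 4.2.3 lists AE recording at Visit 3 ahead of the injection step. Protocol 7.2 makes the investigator responsible only for events after each subject's first dose.

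**SAE period.** The opening sentence of Protocol 7.3 runs SAE collection from dosing to the 3-month follow-up. Its next paragraph requires SAE reporting after the first dose and through follow-up, with no Month 3 end.

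**The concern.** Liposuction is an invasive procedure that every subject undergoes, including controls who receive none of the harvested product. Both documents build the Safety population around it, yet the planned tables begin only at the later injection. A by-group rate of harvest complications would have to be counted by hand from listings, and only if the events were captured in the first place.

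The SAE conflict matters for a different reason. AEs are recorded to Month 12 (JointStem) or Month 6 (control), the study-level rules in Protocol 3.4 count deaths and Grade 3 or higher reactions in the injected joint throughout the trial, and the SAP tabulates SAEs to the end of the study. All of this presumes uniform SAE handling after Month 3. Two sites could follow different sentences of Protocol 7.3 and each be compliant. Safety is half of the stated objective, about 30 subjects are planned and SAP 8.2 plans no DSMB, so a few inconsistently handled events would be visible in the results.

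**Working it through.** The plan states no figure on this point to reproduce. The only planned numbers are those in Protocol 6.2: 30 subjects, 20 JointStem and 10 control (30 × 2/3 = 20; 30 × 1/3 = 10). The check is mainly a comparison of texts.

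**1. Which interval events reach a table?** Take an AE that starts between liposuction and injection and apply SAP 7.1:

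- Known start date, no worsening after injection: listing only.
- Worsens after injection: meets the TEAE definition, so it is tabulated.
- Partial start date whose known year and month (or year alone, if that is all there is) match the first dose: imputed to the first dose date, so it is tabulated.

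The gap is the first case.

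**2. How many tables?** SAP 7.1 lists 6: the overview; TEAEs by SOC and PT; the same by severity; drug-related TEAEs; SAEs by SOC and PT; and TEAEs leading to discontinuation. All sit under the TEAE-only sentence, so 0 of 6 cover first-case events on the plain reading. The SAE row of the overview and the SAE table are not labelled TEAE. If they were meant to be unrestricted, 2 of the 6 would pick up interval SAEs.

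**3. Size of the untabulated window.**

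- Ceiling: 30 subjects × 5 weeks = 150 subject-weeks (20 × 5 = 100 JointStem, 10 × 5 = 50 control). It is a ceiling because 5 weeks is a maximum.
- With 1 month = 365.25/12/7 = 4.348 weeks, the share of time from Visit 2 is at most 5/(5 + 26.1) = 5/31.1 = 16.1% for control to Month 6, and 5/(5 + 52.2) = 5/57.2 = 8.7% for JointStem to Month 12.

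**4. Is at least one interval event likely?** The documents give no liposuction AE rate, so the per-subject rate p is an assumption. P(at least one affected among 30) = 1 − (1 − p)^30:

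| Assumed p | Probability |
|---|---|
| 3% | 59.9% |
| 5% | 78.5% |
| 10% | 95.8% |
| 20% | 99.9% |

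This covers any interval AE, including those in the second and third cases of step 1.

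**5. When does AE capture start?**

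- From randomization: Protocol 3.6.3; Protocol 4.2.3; and the schedule, where AE assessment at Early Termination lacks the footnote that confines other assessments to subjects past Visit 3. SAP 7.1 also presupposes it by listing AEs that are not treatment-emergent.
- After the first dose: Protocol 7.2.

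Both SAE sentences in Protocol 7.3 also start at or after dosing, so neither one reaches a serious harvest complication before injection.

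**6. When does SAE collection end?** Post-injection visits by group (Protocol 3.5.8):

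- JointStem: Visits 4 to 8 = 5. After Month 3: Visits 6, 7 and 8 = 3 of 5. By time, (12 − 3)/12 = 75%.
- Control: Visits 4 to 6 = 3. After Month 3: Visit 6 = 1 of 3. By time, (6 − 3)/6 = 50%.

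The schedule labels Visits 4 to 6 first follow-up and Visits 7 and 8 second follow-up, so the follow-up period does not naturally stop at Month 3. The later sentence of Protocol 7.3 on possibly related events is an additional reporting route, not a further contradiction.

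**The case against.** TEAE-only tables are common practice. Protocol 6.1.6 is one sentence that is silent on timing, and defining the tabulated period is the SAP's job. All AEs are listed, no safety tests are planned, and with about 30 subjects a reader can count interval events from listings. Most of this stands. What remains is the mismatch with a Safety population that both documents anchor at the harvest, and the listing argument works only if Protocol 7.2 does not prevent capture.

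Stronger readings that a reader might infer, and why the documents do not support them:

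- *Every harvest event is kept out of every table, or lost.* Events that worsen, or whose partial dates are imputed to the first dose, are tabulated. The rest are listed if captured.
- *The SAP contradicts Protocol 6.1.6, so its statement in section 9 ("There is no major change in the planned analyses based on the study protocol") is false.* A protocol sentence with no time window is not contradicted by a SAP that sets one.
- *SAEs after Month 3 go unrecorded.* They would still be recorded as AEs, and if the second paragraph of Protocol 7.3 governs, no visits are affected. The visit counts show where the text disagrees. They do not estimate lost events.
- *TEAE percentages are diluted by subjects harvested but never injected, so the denominator should be injected subjects.* SAP 7 runs all safety analyses on the Safety population and Protocol 6.1.1.3 evaluates that cohort for all safety variables. The number never injected is not given and may be zero.

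One more argument is that Protocol 7.1.1 ties an AE to drug use, so a harvest event is not an AE at all. Protocol 3.6.3 and 4.2.3 and the SAP's listing of non-treatment-emergent AEs point the other way.

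**Conclusion.** The point holds in limited form.

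- **Tables.** Harvest AEs with a known pre-injection start date that do not worsen are left out of all 6 SAP tables on the plain reading. The period concerned is at most 150 subject-weeks. The number of events is unknown, because no liposuction AE rate is given.
- **AE start.** Protocol 7.2 conflicts with Protocol 3.6.3, 4.2.3 and the schedule.
- **SAE end.** Protocol 7.3 conflicts with itself for 3 of 5 JointStem visits and 1 of 3 control visits after injection, and its Month 3 end does not fit Protocol 3.4 or the SAP's end-of-study tabulation. What is uncertain is SAE-specific collection, not all capture.

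The conclusion assumes that the SAE rows follow the TEAE-only sentence and that the planned 20 and 10 subjects are harvested. It does not affect the efficacy analyses. It is worth correcting because the correction is cheap and safety is a stated objective.

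**What to change.** 1. **SAP 7.1.** Add one descriptive table of AEs and SAEs from liposuction to injection, by group and overall, on the Safety population. State whether the SAE row of the overview and the SAE table are limited to TEAEs. Leave the denominator as it is.
2. **Protocol.** The sponsor must reconcile 7.2 with 3.6.3, 4.2.3 and the schedule, and the sentences of 7.3 with each other, with the schedule and with 3.4, so that AE collection and SAE collection each have one stated start and one stated end. Which window applies is for the sponsor to decide.

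Cost: one extra table, protocol and SAP wording changes, and possibly slightly higher reported event counts. No new visits are needed. If the sponsor's chosen SAE window is wider than some sites now apply, expedited reporting at those sites would extend with it.
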